# Only to be performed if patient is an inpatient. Otherwise move to Study procedures following discharge

% Nasopharyngeal swabs and blood draws should be collected if local logistical and biosafety procedures allow. Day 1 and 4 and 10 blood and days 1 and 10 NP or OP swabs are preferred if limited.

@ We will attempt to coordinate follow-up clinic visits within 1-2 weeks from hospital discharge to obtain nasopharyngeal and blood biospecimens

& Subject discharged before D7 will be sent home with a pulse oximeter to calculate P/F ratio and a phone call will be made at this time

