stroke. While the rationale for eConsent is different in this case (minimization of disease spread during a pandemic), we believe it is appropriate for the disease and intervention being studied. Critically, the established safety profile of losartan, with minimal side effects of effects on blood pressure in healthy patients without an overactive renin-angiotension-aldosertone system, combined with the close telemedicine and EMR based follow-up methods proposed in this study make the risk : benefit ratio for the alteration of traditional consent process acceptable for participants, providers, and the public.

5.3 *Administration of study drug:* Study drug will be dispensed to bedside nurses twice daily for administration. Patients unable to take the suspension (due to endotracheal intubation) will have it administered via an orogastric or nasogastric tube, or G-tube. If the patient is unable to receive the study drug for respiratory distress, we will allow for +/- 3 hours from the scheduled time of drug administration. If this is not possible, the patient will not receive that dose, and this will be tracked.

5.4 *Patient follow-up:* Participants will receive remote telemedicine, phone, or in person evaluation by trained study personnel every day for the 10 days of the intervention period to monitor for the development of complications as well as day 15. In addition, electronic medical record labs and notes will be monitoring for the development of AE and SAEs. Data will be documented into a Redcap database. The coordinators will have patients complete 2 surveys at enrollment, day 4, day 10, and day 28 (both attached in supplement), if the patient can cooperate. If not, the reason for failure to complete the survey will be recorded. Surveys conducted within 1 day of the time point will be counted as qualifying and not missing. Patients will be contacted at day 28 (+/3 days) and 90 (+/- 3 days) for intermediate term outcomes. If follow-up procedures are not completed due to inability (patient unavailable or intubated), or due to loss to follow-up, these will not be counted as protocol deviations.

5.5 *Pharmacokinetics:* Patients undergoing this voluntary substudy will have up to another 9 mL of total blood drawn (30 mL total day 1 instead of 21-24 mL day 1. The remainder of the samples will be the same for the duration of the study). Blood will be processed, frozen at -80 C until shipping to [name] at the University of Nebraska for analysis.

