## MEDICAL PROTOCOL (HRP-590)

SHORT PROTOCOL TITLE: Randomized control trial of losartan for inpatients with COVID-19

VERSION DATE:22APR2020

Additional labs (pregnancy, Cr, potassium) if applicable	X																	
Randomize subject	X																	
POST-RANDOMIZATION																		
Enrollment Day 0 CRFs	X																	
Dispense / administer study drug**		X	X	X	X	X	X	X	X	X	X	X	X	X	X	X	X	X
MINIMUM STUDY PROCEDURES (while inpatient, if applicable) #																		
Daily CRFs		X	X	X	X	X	X	X	X	X	X	X	X	X	X	X	X	X
Creatinine, Potassium\$	X\$	X\$	X	X\$	X	X	X	X\$	X	X	X	X	X	X	X	X	X	X
SOFA score assessment	X	X	X	X	X	X	X	X	X	X	X	X	X	X	X	X	X	X
Estimated P/F	X	X	X	X	X	X	X	X&	X	X	X						X	
Ordinal scale	X	X	X	X	X	X	X	X	X	X	X	X	X	X	X	X	X	X
Blood draws%		X	X		X		X		X		X		X				X	
Nasopharyngeal or oropharyngeal swabs%		X			X				X		X						X	
Adverse event assessment		X	X	X	X	X	X	X	X	X	X	X	X	X	X	X	X	X
PROMIS Survey	X			X						X							X	
Short Form 12 Health Survey	X			X						X							X	
STUDY PROCEDURES FOLLOWING DISCHARGE (if applicable)																		
Assessment of Hospitalization																	X	X
Estimated P/F&																	X	
Follow-up biospecimens (NP/OP swab + blood draw)																	@	
Electronic medical record / death index review																		X
Adverse event assessment																	X	X
PROMIS Survey				X						X							X	
Short Form 12 Health Survey				X						X							X	
OPTIONAL STUDY PROCEDURES																		
Pharmacokinetic Lab Draw***		X																

\*Within 48 hours of hospital admission or a positive test result, whichever is later,

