### 16.2 Identify the source of Private Health Information you will be using for your research (Check all that apply)

- I will use the Informatics Consulting Services (ICS) available through CTSI (also referred to as the University's Information Exchange (IE) or data shelter) to pull records for me

MEDICAL PROTOCOL (HRP-590)

SHORT PROTOCOL TITLE: Randomized control trial of losartan for inpatients with COVID-19

VERSION DATE:22APR2020

- I will collect information directly from research participants.
- I will use University services to access and retrieve records from the Bone Marrow Transplant (BMPT) database, also known as the HSCT (Hematopoietic Stem Cell Transplant) database.
- I will pull records directly from EPIC.
- I will retrieve record directly from axiUm / MiPACS
- I will receive data from the Center for Medicare/Medicaid Services
- I will receive a limited data set from another institution
- Other. Describe: CTSI's BPIC will be used to pull structured data directly from EPIC into redcap (ED vitals, labs, etc.), or data will be transcribed by coordinators into our Redcap research database. Study coordinators will contact patients daily to obtain data and will input it directly into the Redcap research database.

16.3 *Explain how you will ensure that only records of patients who have agreed to have their information used for research will be reviewed:* Study coordinators and BPIC will review if patients have opted out of research by using the opt-out flag within Epic to determine research status. Only patients that have opted-in to research or have expressed that they wish to delay opt-out status will be included in this study.

16.4 *Approximate number of records required for review:* 220.

16.5 *Please describe how you will communicate with research participants during the course of this research. Check all applicable boxes:*

- This research involves record review only. There will be no communication with research participants.
- Communication with research participants will take place in the course of treatment, through MyChart, or other similar forms of communication used with patients receiving treatment.
- Communication with research participants will take place outside of treatment settings. If this box is selected, please describe the type of communication and how it will be received by participants.

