### 18.2 Adverse events reporting

- *Definition of an Adverse Event (AE):* An AE is any symptom, sign, illness, or experience that develops or worsens in severity during the course of the study but does not necessarily have a causal relationship with study agent/intervention or procedures. A clinical trial adverse event is defined as any untoward medical event associated with the use of a drug or study procedure. The Investigators will determine daily if any adverse events occur during the period from enrollment (signing of the informed consent) through study day 15. Investigators will determine if the event is serious or related to the study drug. The rationale for this time window is the half-life of 2 hours for losartan and 6-9 hours for its metabolite. Even in the setting of impaired clearance, 3 days after study drug cessation is more than adequate to help to define the period at risk from losartan. Abnormal results of diagnostic procedures are considered to be AEs if the abnormality:

- results in study withdrawal,

MEDICAL PROTOCOL (HRP-590)

SHORT PROTOCOL TITLE: Randomized control trial of losartan for inpatients with COVID-19

VERSION DATE:22APR2020

- is associated with a serious adverse event (SAE),
- leads to additional treatment or to further diagnostic tests, or
- is considered by the Investigator to be of clinical significance.

- **Definition of a Serious Adverse Event:** Adverse events are classified as serious or non-serious. An SAE is any AE that is:

- *Fatal,*
- *life-threatening,*
- *requires or prolongs a hospital stay,*
- *results in persistent or significant disability or incapacity,*
- *a congenital anomaly or birth defect, or*
- *an important medical event.*

Important medical events are those that may not be immediately life threatening, but are clearly of major clinical significance. They may jeopardize the subject, and may require intervention to prevent 1 of the other serious outcomes noted above. For example, drug overdose or abuse, a seizure that did not result in in-patient hospitalization, or intensive treatment of bronchospasm in an emergency department would typically be considered serious. Serious adverse events will be collected during the first 15 study days, regardless of the investigator's opinion of causation. Thereafter, serious adverse events are not required to be reported unless the investigator feels the events were related to either study drug or a protocol procedure.

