- **Response to possibly, probably, or definitely related AEs and SAEs:** SAEs determined to be probably or definitely related will prompt discontinuation of study drug. AEs determined to be probably or definitely related with prompt a) decrease in study drug from twice a day to once a day if currently dosing twice daily, b) discontinuation of study drug if only taking once daily, or c) discontinuation for study drug at the discretion of the investigator.
- **Anticipated Adverse Events:** Adverse events are not expected from any of the study procedures. We do not expect any serious adverse events due to losartan.
- **Recording and Documentation**
  - At each contact with the subject, personnel must seek information as to discomforts or adverse experiences by specific questioning and, as appropriate, by examination. This will typically occur via phone or telemedicine due to concerns regarding infectious contagion. Information about AEs to be recorded includes event description, time of onset, investigator assessment of severity, relationship to Study Agent(s)/Intervention(s), and time of resolution/stabilization of the event. All AEs occurring during the study period (from time of consent signing to study day 15) must be documented appropriately regardless of relationship to study products or procedures unless included on the list of clinical outcomes that may be exempt from adverse outcomes reporting as part of the study protocol and outcomes. Information on all identified AEs will be recorded within 5 days of recognition in the appropriate AE module of the case report form (CRF) on Redcap, and within 24 hours in the event of a SAE.

18.3 **Data Safety Monitoring:** A data safety monitoring board (DSMB) has been convened and includes 4 individuals meeting the key element criteria below, and includes a biostatistician with prior clinical trials DSMB experience. The DSMB will follow the guidance as outlined in the application and the attached charter unless there is a compelling, unanticipated reason to deviate from these rules. Data regarding the primary outcome (hospitalization) will be reported to the DSMB continuously, consistent with continuous study monitoring principles. The DSMB may recommend stopping the trial early only for safety, following these guidelines:

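### The table of events confines daily adverse event assessment to inpatients, while sections 5.4 and 18.2 set it by calendar day, so capture of mainly non-serious events could depend on length of stay

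*Combined protocol and SAP*

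**What the plan says.** **Table of events (section 5.6).** The daily case report forms and an AE assessment row marked on every study day stand under the block heading "MINIMUM STUDY PROCEDURES (while inpatient, if applicable". The footnote to that heading reads "Only to be performed if patient is an inpatient. Otherwise move to Study procedures following discharge". The next block, "STUDY PROCEDURES FOLLOWING DISCHARGE (if applicable", has its own AE row, marked only in the last two columns.

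**Section 5.4.** Study personnel evaluate participants by telemedicine, by phone or in person "every day for the 10 days of the intervention period to monitor for the development of complications as well as day 15". Labs and notes in the medical record are also watched for AEs and serious AEs (SAEs).

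**Section 18.2.** "The Investigators will determine daily if any adverse events occur during the period from enrollment (signing of the informed consent) through study day 15". It adds: "All AEs occurring during the study period (from time of consent signing to study day 15) must be documented appropriately regardless of relationship", apart from listed clinical outcomes that are tracked separately. For serious events: "Serious adverse events will be collected during the first 15 study days".

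**Section 16.2.** "Study coordinators will contact patients daily to obtain data", with no limit to inpatients.

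No section says which schedule governs after discharge. Section 15 gives no window or denominator for AE counts.

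**The concern.** The table is the page that site staff work from. Read literally, it ends daily AE assessment at discharge, which may fall well inside the 15-day AE window. A patient still in hospital is then asked every day, while a patient at home is asked at the marked contacts and at whatever other contacts happen to occur.

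Discharge happens after randomisation, and hospital length of stay is one of the resource-utilisation endpoints in section 3.3. The trial hopes losartan will improve respiratory failure, so stay may differ by arm. If losartan shortens stay, its patients are observed less intensively and may appear to have fewer AEs at the same true rate. If it lengthens stay, the distortion runs the other way. Section 3.4 itself notes that reliance on AE reporting can introduce bias.

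**Working it through.** The plan gives no figure to reproduce, so the first step is to compare the texts.

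**1. Schedules after discharge, within days 1 to 15**

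| Source | Rule | Does discharge change it? |
|---|---|---|
| 5.6, inpatient block and footnote | AE assessment every day | Yes, the block ends |
| 5.6, post-discharge block | AE assessment in the last two columns | Applies only after discharge |
| 5.4 | Each of 10 days, and day 15 | No |
| 18.2 | AEs determined daily through day 15 | No |

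The table's column header is damaged in the text available: it runs to day 17, although follow-up goes to days 28 and 90. The dates of the last two columns therefore cannot be read. Neither is a daily contact, so the comparison holds. In the same block the PROMIS and SF-12 rows are marked in earlier columns, where the AE row is blank. The block can therefore show earlier contacts, and the gap in the AE row does not come from the layout.

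**2. Can the texts be reconciled?** Section 4.1 ends treatment at discharge, so the intervention period in 5.4 might be taken to end there too. But 5.4 names 10 days and allows phone contact. Section 18.2 runs to day 15 whatever the discharge date, and its rationale reckons with a period after the drug stops. Section 18.2 cannot be squared with a table that ends daily assessment at discharge.

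**3. How large could the effect be?** This is an illustration resting on assumptions. Let the true daily AE rate be constant and equal in both arms. Let L1 and L0 be mean inpatient days (at most 15) on losartan and placebo, and c the share of post-discharge AEs captured, relative to in-hospital capture. Then

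apparent ratio = [L1 + c(15 − L1)] / [L0 + c(15 − L0)].

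Take L0 = 10, the average stay given in the rationale for endpoint timing (section 3). That figure counts from admission, and randomisation may come later. Take L1 = 8, an assumption.

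| c | Calculation | Ratio |
|---|---|---|
| 0 | 8 / 10 | 0.80 |
| 0.25 | 9.75 / 11.25 | 0.87 |
| 0.5 | 11.5 / 12.5 | 0.92 |
| 0.75 | 13.25 / 13.75 | 0.96 |
| 1 | 15 / 15 | 1.00 |

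If L1 = L0, the ratio is 1.00 for every c. The documents give neither c nor any expected difference in stay.

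**The case against.** The strongest reply is that the table does not leave discharged patients unobserved. Section 18.2 requires staff to ask specifically about adverse experiences at every contact. The table also keeps a day-7 call for anyone discharged before then, and survey contacts after discharge. Section 5.4 adds record monitoring. Section 18.2 asks investigators to determine AEs daily, which record review might satisfy without a call. On this view 5.4, 16.2 and 18.2 fit together, and the outlier is one table block with its footnote.

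Much of this stands. A reader might infer from the table that AE collection stops at discharge, or that patients at home are asked no more than twice; the day-7 call, the surveys and the rule on questioning at each contact contradict both. A reader might also infer that the SAE comparison and the reports to the monitoring board are seriously biased, and the documents do not support that either. SAEs have their own 15-day collection. Deaths, ventilatory support and vasopressor use are reported promptly. After discharge such events would mean readmission or death, which record review, the hospitalisation assessment and the death-index check are there to find. The safety endpoints in section 3.3 are hypotension and renal failure, not AE counts.

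The reply does not remove the difference in intensity. Incidental contacts are not daily contacts, and a mild event at home may never reach the record. Section 5.4 also does not count follow-up missed because a patient is unavailable or lost as a protocol deviation, so such gaps may not be noticed.

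**Conclusion.** The inconsistency is real and should be corrected. Under the table, detection of AEs, chiefly non-serious ones, would vary with length of stay; under 5.4 and 18.2 it is set by the calendar.

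Bias between arms needs two conditions: that stay differs by arm, and that capture is lower after discharge. The documents fix neither, so no size can be given. The range of 0.80 to 1.00 rests on assumed stays of 8 versus 10 days, a constant AE rate and equal true risk. The constant rate is itself doubtful, because study drug stops at discharge. A reader might take 0.80 as the expected understatement, but it requires that nothing at all be captured after discharge, and the table's own post-discharge AE row rules that out.

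The point concerns the completeness and comparability of the AE tables. It does not touch the primary endpoint and bears only weakly on SAEs and deaths.

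**What to change.** - Amend the post-discharge block and its footnote so that AE and SAE assessment is marked daily to day 10 and at day 15, by phone or telemedicine, for every randomised patient who is alive and has not withdrawn from follow-up, whether or not discharged. Use the same AE form as for inpatients.
- Align section 18.2 with that calendar. State what daily determination means on days without a contact, and have the day-15 contact ask about days 11 to 15.
- In section 15, state that AEs are reported by arm over the fixed window to day 15. If inpatients continue to be assessed daily on days 11 to 14, add a supportive table for days 1 to 10, where the schedule would be the same for everyone.

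The cost is a table correction and a few short calls per early-discharged patient. Sections 5.4 and 16.2 already describe these contacts, so no new procedure is added.

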- Evidence of bacterial co-infection
- Glasgow coma scale (daily, if available)
- Death (with date, if applicable)
- Study withdrawal, with date and time (if applicable)

- Final outcome follow-ups will be determined through a combination of patient report, electronic medical record review, and review of the social security death index (SSDI).
- All data will be stored in a password protected Redcap database, with customizable tiered access and an audit trail. All protected health information (PHI) will be marked with a PHI tag that will prevent export, so only deidentified data can be exported from the database. Only deidentified data with no PHI will be exported for analysis.
- Nasopharyngeal or oropharyngeal swabs (day 1,4,8,10,15); 30 patients will receive blood draws for pharmacokinetic analysis (day 1, hours 2, 4, and 6) and patients will provide blood samples for RAAS, RNASeq, flow cytometry, and cytokine assays, collected by study personnel or bedside nurse and placed in pre-packaged transport containers to be collected by biosafety-trained transporters, transported and processed to the University of Minnesota's BSL-3 laboratory noted above, and frozen at -80 C until later analysis for local sites. Blood samples will not exceed 30 mL day 1, and will equal ~21-24 mL on days 2, 4, 6, 8, 10, and 15). All

biospecimens will be labeled with a deidentified patient ID number to prevent inadvertent disclosure of PHI. Participants will be given the opportunity to contribute to an optional study using genetic material for future studies of patient-level responses to COVID-19. These samples will likewise be deidentified, but are theoretically identifiable biologic information.

- Cytokine assays will be conducted by [name]'s laboratory at the University of Minnesota
- RAAS pathway assays will be conducted at the Wake Forest Hypertension and Vascular Research Biomarker Analytical Core
- Pharmacokinetics will be conducted at [name]'s Antiviral Pharmacology Laboratory at the University of Nebraska

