1.4 *Justification of the primary outcome:* This trial seeks to mitigate lung injury from Covid-19 rather than treating the viral infection. Most patients present to the hospital secondary to dyspnea and pneumonia, and the primary mechanism of death is via respiratory failure progressing to multi-system organ failure. Prevention of progression of acute lung injury with an angiotensin receptor blocker such as losartan may decrease estimated P/F ratio, a validated measure of lung dysfunction that accounts for differences in the level of ventilatory support. We considered respiratory SOFA score, but this crude ordinal measurement is estimated off of the estimated P/F ratio, which will provide a more precise measurement of the same physiology. **Estimated P/F is a clinically relevant outcome not only to patients, but also to the healthcare system due to overwhelming surge of patients straining hospital resources** which not only puts patients with COVID-19 at risk, but also those admitted to the hospital for other reasons.

- *Rationale for the timing of the primary endpoint:* The average time from hospitalization to mechanical ventilatory support is 2-3 days, and average length of hospital stay is 10 days. We considered a 3 day outcome time point to minimize the need for home measurement and early death. However, >24 hours is required to reach steady state levels of drug, and 3 days is likely too early to detect a treatment benefit. We also considered 10 days, but this increases competing risks and decreases the sensitivity and strength of using the continuous primary outcome but increasing the proportion of patients who either die or recover, skewing the data. We

believe 7 days to represent the optimal balance of these competing concerns.

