**3.4 Justification of the secondary outcomes:** Patients severely infected with respiratory dysfunction may be at increased risk of volume depletion, acute kidney injury, or the development of hypotension, so we will systematically track these measured instead of relying upon adverse event reporting which introduces the potential for bias. We will measure P/F ratios daily in case our choice of 7 days proves incorrect. SOFA score is a validated measuring of organ failure in critically ill populations that can be determined. Death is clinically important, but we do not believe our sample size is adequately powered to detect a difference in this outcome. Resource utilization and respiratory support are critical in surge capacity situations and of relevance to this disease process. Validated study instruments to assess dyspnea and physical function will assess patient-centered outcomes and strengthen the biologic plausibility of the intervention. The 7-point ordinal scale described is used by other ongoing Covid-19 clinical trials and will allow harmonization of the trial results. Changes in viral load are important to assess the theoretical possibility of losartan induced ACE2 expression leading to increased viral entry, propagation, and shedding.

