## **11.0 Local Recruitment Methods**

*11.1 Recruitment Process:* See section 5.0

*11.2 Identification of Potential Participants:* See section 5.0

*11.3 Recruitment materials:* N/A

*1.5 Payment:* Patients will be eligible for a \$25 gift card for their time to return for the 15-day blood draw for renal function testing if allowed by local site.

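### The last viral-load sample is timed from discharge in the table of events but set at study day 15 elsewhere, so for discharged patients its study day depends on length of stay, and the analysis does not allow for this

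*Combined protocol and SAP*

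**What the plan says.** Section 1.6 gives fixed study days: "Nasopharyngeal or oropharyngeal swabs (day 1,4,8,10,15". It says that blood volume "will equal ~21-24 mL on days 2, 4, 6, 8, 10, and 15". The payment item in section 11.0 offers a gift card to patients who "return for the 15-day blood draw for renal function testing".

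The table of events in section 5.6 works differently. Footnote # restricts the scheduled procedures: "Only to be performed if patient is an inpatient. Otherwise move to Study procedures following discharge". In the post-discharge block the only specimen entry carries footnote @: "We will attempt to coordinate follow-up clinic visits within 1-2 weeks from hospital discharge to obtain nasopharyngeal and blood biospecimens". As far as the column layout can be read, @ stands in the same column as the last scheduled inpatient swab and blood draw, so it appears to replace that sample.

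Change in viral load is a secondary endpoint (section 3.3) with no time point of its own. Section 3.4 gives its purpose: "Changes in viral load are important to assess the theoretical possibility of losartan induced ACE2 expression", with more viral entry and shedding as the feared result. Hospital length of stay is also a secondary endpoint. Section 15.1 compares secondary endpoints by a t-test allowing unequal variances or by chi-square.

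**The concern.** Two rules for one sample cannot both be followed. Under footnote @, the study day of a discharged patient's last swab is set by when that patient went home, which treatment may affect. Viral load in an acute infection can be expected to fall with time, so a patient sampled earlier tends to show more virus.

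If losartan shortened stay and its patients were sampled earlier as a result, the last value could look like the shedding harm that section 3.4 wants to detect. If losartan lengthened stay, real harm could be partly hidden. Nothing in section 15.1 would separate timing from effect. Its adjusted analyses concern baseline imbalances, and sampling day is not a baseline variable. Its joint model covers P/F ratio and death, not viral load.

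**Working it through.** The plan gives no figure for the viral-load comparison, so there is none to reproduce.

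**1. Window by discharge day.** For discharge on study day d, footnote @ read as 7 to 14 days gives sampling on day d+7 to d+14. Day 15 lies inside when d+7 ≤ 15 ≤ d+14, that is, for d from 1 to 8.

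| Discharge day d | Sampling window | Contains day 15? |
|---|---|---|
| 2 | 9-16 | yes |
| 8 | 15-22 | yes |
| 10 | 17-24 | no |
| 14 | 21-28 | no |

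From the earliest day for d = 2 to the latest for d = 14 is 28 − 9 = 19 days.

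**2. Where a typical patient falls.** The rationale for endpoint timing in section 3 states that "average length of hospital stay is 10 days". With randomisation 0-2 days after admission, d is about 10 − 2 = 8 to 10 − 0 = 10, and the window runs from days 15-22 to days 17-24. Section 8.1 also lets the 48 hours run from a positive result if that comes later, so d can be smaller. For d = 7 the window is days 14-21.

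**3. Spread of sampling days (simulation).** These assumptions are not in the documents: discharge day gamma-distributed with mean 10, rounded up to a whole day; coefficient of variation (CV) 0.4, 0.5 or 0.7; outpatient sample uniform over the 7-14 day window; patients not discharged by day 14 sampled on day 15.

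| CV | Discharged by day 14 | Window contains day 15 | Mean last-sample day (5th-95th percentile) | Discharged before day 8 / day 10 |
|---|---|---|---|---|
| 0.4 | 85% | 34% | 19.0 (14.3-25.1) | 24% / 45% |
| 0.5 | 81% | 40% | 18.3 (13.4-24.9) | 31% / 48% |
| 0.7 | 77% | 47% | 17.3 (11.8-24.4) | 41% / 54% |

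The last column is a separate matter. Those patients miss the fixed day-8 or day-10 inpatient sample because scheduled sampling stops at discharge.

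**4. Difference between arms.** With the same stay in both arms, the mean shift in sampling day is 0. With a shorter mean stay in one arm, sampling moves earlier in that arm by:

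| CV | 1 day shorter: all / discharged | 2 days shorter: all / discharged |
|---|---|---|
| 0.4 | 0.18 / 0.51 days | 0.59 / 1.15 days |
| 0.5 | 0.12 / 0.42 days | 0.40 / 0.92 days |
| 0.7 | 0.09 / 0.28 days | 0.26 / 0.62 days |

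Spurious difference = shift × daily decline, with an assumed decline of 0.1-0.3 log10 per day:

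- All patients: 0.09 × 0.1 = 0.01 to 0.59 × 0.3 = 0.18 log10.
- Discharged patients: 0.28 × 0.1 = 0.03 to 1.15 × 0.3 = 0.34 log10.

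**5. Sensitivity to mean discharge day.** The same simulation with mean 8 gives all-patient shifts of 0.28-1.48 days, or 0.28 × 0.1 = 0.03 to 1.48 × 0.3 = 0.44 log10. With mean 12, the all-patient shift is close to zero and mostly slightly later (up to 0.16 days), although discharged patients are still sampled earlier. The reason is that a patient still in hospital is sampled on day 15, while one discharged on day 14 is sampled on days 21-28, at least 6 days later. Shortening stay moves some patients from the first group to the second.

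**The case against.** The strongest defence is that this is one best-effort sample. Footnote @ promises only an attempt, and section 6.2 accepts missed biospecimens because of biosafety barriers. Where collection is limited, footnote % puts swabs on days 1 and 10 first, and the outpatient sample is not among the preferred ones. Linking it to a clinic visit is a practical choice. The footnote could also mean any time within two weeks of discharge, in which case day 15 is reachable for discharge on days 1 to 14. All of this is fair, and it limits the importance of the point. It does not remove the conflict with section 1.6, and on either reading the study day still follows the discharge date.

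A reader might infer four stronger things that the documents do not support:

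- **That the whole viral-load comparison is confounded with time.** Inpatient samples on days 1, 4, 8 and 10 keep fixed study days; only the post-discharge sample floats. Directional bias also needs a treatment effect on stay, which is unknown.
- **That a 2-day difference in stay shifts sampling by 2 days, giving 0.2-0.6 log10.** Patients still in hospital on day 15 are sampled that day, so the shift is smaller.
- **That day 15 is at best the first day of a typical patient's window.** This treats the average stay as everyone's and overlooks randomisation timed from a later positive test.
- **That renal failure is observed only in hospital.** Section 11.0 describes a return blood draw at day 15 for renal function. What is missing is a creatinine or potassium row in the post-discharge block of the table.

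**Conclusion.** The point holds for the last, post-discharge sample. Section 1.6 and section 11.0 conflict with footnotes # and @, and the viral-load analysis has no rule for sampling day, no window for day 15 and no rule assigning the outpatient sample to a nominal day.

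If losartan does not affect stay, the consequence is extra variability. If it does, the bias is about 0.01-0.18 log10 overall and 0.03-0.34 among discharged patients, under the assumed mean discharge day of 10, a 1-2 day shorter stay and a 0.1-0.3 log10 daily decline. Other plausible stay distributions change the size and, over all patients, can change the direction. None of these figures can be taken from the documents. Missing day-8 and day-10 samples after discharge are a related, outcome-dependent gap that retiming the last sample does not close.

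**What to change.** 1. Reconcile section 1.6, the table of events with footnotes # and @, and section 11.0. Time the same best-effort outpatient swab and blood sample to study day 15, with a stated window counted from randomisation whatever the discharge date.
2. Record the actual date and study day of every specimen.
3. Give the viral-load endpoint a time point, and prespecify an analysis by actual study day since randomisation, for example a longitudinal mixed model. State how samples missing after discharge or death are handled.
4. Separately, reconcile section 11.0, which describes the day-15 draw as renal testing, with the post-discharge block of the table, which lists no creatinine or potassium.

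With all patients sampled on day 15, the timing difference between arms would be zero; within a window it is limited by the window's width and handled by step 3. The cost is mainly wording: the visit remains a single one. The drawback is that some patients will miss a fixed window, and those discharged shortly before day 15 must return soon after going home.
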